4. STUDY OBJECTIVES

Primary Objective

To evaluate the effectiveness of isCGM with CDE education and feedback on glycemic control at 12 weeks, in adults with type 2 diabetes and uncontrolled HbAc ($> 7.0\%$) not on insulin therapy.

Secondary Objectives

To determine the feasibility of recruiting adults with diabetes in Edmonton-area to a trial of glucose self-monitoring and education.

To determine the effectiveness of isCGM with CDE education and feedback on patient self-management of diabetes, measured using patient reported instruments for diabetes-related quality of life, diabetes treatment satisfaction, diabetes self-management empowerment, diet, and physical activity – at 6 weeks and at 12 weeks.

To determine the safety of isCGM with CDE education and feedback with respect to emergency department visits or hospitalizations, and isCGM-specific reactions (e.g.: skin reactions).

To understand the reasons *why* or *how* isCGM with CDE education is effective or ineffective from the perspective of involved participants and their providers.

To evaluate the effectiveness of isCGM with CDE education and feedback on glycemic control at 24-52 weeks (post-trial observational follow-up).

5. isCGM (INTERMITTENTLY SCANNED CONTINUOUS GLUCOSE MONITOR) – DESCRIPTION OF TECHNOLOGY

Technology – The only isCGM on the market at this time is the FreeStyle Libre 2 system produced by Abbott. FreeStyle Libre 2 sensors use a subcutaneous, wired enzyme glucose-

sensing technology, factory-calibrated to detect glucose levels in *interstitial* fluid by way of a thin filament implanted under the skin. The sensors are water-proof, affix to the skin by medical adhesive, last 14 days each, and are roughly the size of two stacked quarters. They measure interstitial glucose every minute, with readings stored in 15-minute intervals. Patients can scan sensors on-demand, using either a near-field communication-enabled smart phone or the FreeStyle Libre 2 Reader, to receive a glucose result along with historic results for the preceding 8 hours. The FreeStyle Libre 2 system is fully marketed in Canada; in 2020, it's predecessor, the similar FreeStyle Libre flash glucose monitoring system, had over 2 million users internationally.³²

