10. STUDY OUTCOMES AND VARIABLES

Case report forms are provided in Appendix 5. These will be translated into electronic documents to be completed by participants via a password protected webportal (EpiCore).

Primary Outcome:

- Change in HbA1c at 12 weeks compared to baseline.

Secondary Outcomes:

- Feasibility of recruitment
 - Participant referral, screening, and randomization rates over time
 - Reasons for inclusion / exclusion of all participants referred.
- Change in scores at 6 and 12 weeks compared to baseline, on the patient-reported outcomes shown in Table 1, below.
- isCGM participants only – change in time-in-target range, coefficient of variation, and glucose management indicator at 12 weeks compared to baseline.

Table 1: Patient-Reported Outcomes

Outcome	Instrument	Number of items
Diabetes treatment satisfaction – Status score	Diabetes Treatment Satisfaction Questionnaire (DTSQs) ³⁷ (weeks 6 and 12)	8
Diabetes treatment satisfaction – Change score	Diabetes Treatment Satisfaction Questionnaire (DTSQc) (week 6 only)	
Self-management empowerment	Diabetes Empowerment Scale – Short Form (DES-SF) ³⁸ (weeks 6 and 12)	8
Diabetes-related distress	Problem Areas in Diabetes (PAID) Questionnaire ³⁹	20
Diet	UK Diabetes and Diet Questionnaire (UKDDQ) ⁴⁰ (weeks 6 and 12)	25
Physical activity	International Physical Activity Questionnaire (IPAQ) short form ^{41,42} (weeks 6 and 12)	7
Health status	Euroqol EQ-5D-5L (weeks 6 and 12)	5

* In addition to collection at baseline.

Safety outcomes at 12 weeks:

- Any adverse events (serious and non-serious) occurring from baseline to 12 weeks will be identified and tracked at the 12 week study visit by patient interview, and reviewed

by study investigators to determine whether clinically attributable to diabetes, diabetes management, or isCGM. isCGM issues (e.g.: skin reactions) will be specifically sought.

- Emergency department visits or hospital admission for any reason, identified from patient interview and from NetCare review.

Qualitative Outcomes: Semi-structured interviews will undergo thematic analysis using constant comparative methods. The starting point will be the participant and provider experience with isCGM or enhanced usual care, with a particular focus on barriers and enablers of effectiveness (see Appendix 6, interview guides). Semi-structured interviews will take place for participants after trial completion (from 12-24 weeks).

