- *Limited trial period of 12 weeks.* There is the possibility that insufficient time may have elapsed by the 12 week study HbA1c to see the effect of the intervention, since the 12 week HbA1c may be influenced by blood glucose exposure early in the trial period, before isCGM-based changes are made. Additionally, the 12 month outcome will not be able to speak to the sustainability of any isCGM benefits detected. We have designed a post-trial observational follow-up to address the longer term outcomes of episodic isCGM, recognizing that the follow analysis will no longer benefit from the expected confounder balance of randomization, as participants who consent to data linkage and who have HbA1c measurements post-trial will represent a non-random subset of those initially randomized.
- *Limited support to titrate anti-hyperglycemic medications.* The presumptive mechanism for any improvement in glycemic control is improved diet and lifestyle modification in adults randomized to isCGM. An alternative mechanism may be more rapid medication titration based on isCGM data, instead of HbA1c measurements, which are recommended at intervals no less than 90 days. While the

CDE algorithm (currently under development) may have a role for CDE-to-provider suggestions for medication changes, the intervention is not intended to provide further support or practice change related to provider prescribing (e.g.: decision support, alternate prescribers, provider training).

- *Sample size still has a 20% risk of type 2 error* – Our study is powered to detect a 0.5% difference in HbA1c at a power of 80%. The type 2 error rate (failure to detect a difference on such a difference truly exists) is still 20%, though may be slightly lower if loss-to-follow-up is minimized and recruitment approaches the full 100 participants.

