Appendix 6: Qualitative Sub-Study Interview Guides

iCUDE Trial Qualitative Sub-Study

Interview Guide

Interview Guide (Group 1: Trial Patients Randomized to Intervention)

I would like to start by thanking you for participating in this interview. I am interested in your perspectives regarding the FreeStyle Libre 2 continuous glucose monitor and your visits with the diabetes educator. Before we start our interview, I would like to ask you not to use names of people or institutions that may identify them. We will also remove all identifying information from the transcripts.

1. Did you have any thoughts or expectations about what using the FreeStyle Libre 2 would be like before you started it?
2. Can you tell me about your experience using the Libre 2 for the first time?
Probes: Was it easy or difficult to start using? What do you think about being able see your blood sugar on your cell phone? What did you think of your blood sugars the first day you measured them? How did they make you feel? Did you know what to make of them, or what to do about them?
3. What changes did the Libre 2 lead to in terms of what you eat or what you do during the day? How difficult was it to make those changes?
Probes: Can you think of anything that helped you make those changes? Anything that might have made it harder to make those changes?
4. Has the Libre 2 changed how you think or feel about your diabetes?
5. What kind of support or resources did you have to help with your diabetes before this trial?
6. Can you tell me about the kind of impact meeting with the diabetes educator had on you?
Probes: How long was the encounter? How did it feel talking to the diabetes educator? What did you learn during the encounter? Did you make a plan? What did you like best about the encounter? What would you like to be different?
7. Can you tell me about the kind of impact meeting with the diabetes educator had on your ability to use the Libre 2? To look after your diabetes?
Probes: How about in terms of changes to your diet and activity?
8. Was the second educator encounter different from the first?
Probes: Were there things you learnt that were different in the second encounter, from the first? What would the perfect number of encounters be? How far apart should they be?
9. Is the FreeStyle Libre 2 something you'd consider using again in the future? Why or why not?
10. Do you have goals for your diabetes moving forward?

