Probes: Can you describe your goals? What do you think about these goals? How optimistic are you that you will be able to follow through with your goals?

Version (1): March 24, 2022

1

11. Is there anything else you would like to share about using the Libre 2 or meeting the diabetes educator?

Thank you very much for speaking with me. We would be pleased to offer you a small amount of money (\$20) in appreciation for your time. You can expect it in the mail – please let us know if you don't receive it.

Interview Guide (Group 2: Trial Patient Randomized to Enhanced Usual Care)

I would like to start by thanking you for participating in this interview. I am interested in your perspectives about looking after your diabetes and your visits with the diabetes educator. Before we start our interview, I would like to ask you not to use names of people or institutions that may identify them. We will also remove all identifying information from the transcripts.

1. Do you know how well your diabetes was looked after before you met the educator? How did you feel about your diabetes before you met the educator?
Probes: Were you doing anything in particular to make your diabetes better, or to keep it from getting worse? What kind of support or resources did you have to help with your diabetes?
2. Can you tell me about the kind of impact meeting with the diabetes educator had on you?
Probes: How long was the encounter? How did it feel talking to the diabetes educator? What did you learn during the encounter? Did you make a plan? What did you like best about the encounter? What would you like to be different?
3. Was the second educator encounter different from the first?
Probes: Were there things you learnt that were different in the second encounter, from the first? What would the perfect number of encounters be? How far apart should they be?
4. Did you start measuring your blood sugars at any time during the trial? Do you feel that measuring your blood sugars could have been useful?
5. Do you have goals for your diabetes moving forward?
Probes: Can you describe your goals? What do you think about these goals? How optimistic are you that you will be able to follow through with your goals?
6. Is there anything else you would like to share about meeting the diabetes educator?

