Thank you very much for speaking with me. We would be pleased to offer you a small amount of money (\$20) in appreciation for your time. You can expect it in the mail – please let us know if you don't receive it.

Interview Guide (Group 3: Providers)

I would like to start by thanking you for participating in this interview. I am interested in your perspectives regarding looking after adults with early diabetes – those who are not on insulin, but who need additional blood sugar lowering to get to target. Specifically, I want to talk about using the FreeStyle Libre 2 continuous glucose monitor with these patients. Before we start our interview, I would like to ask you not to use names of people or institutions that may identify them. We will also remove all identifying information from the transcripts.

1. What is your previous experience looking after patients using the Libre or Libre 2 CGM?
2. What difference did the Libre 2 make for our trial patients who were not on insulin?
Would you consider the Libre 2 useful or not useful, in this population? Why or why not?
Probe: (If not useful, then what would the Libre 2 being useful look like?)
3. Are there patient factors that determine whether the Libre 2 is useful for an individual or not? What are they?
Probe: Are they related to knowledge? Skill? Motivation? Supports? Environment? Diet? Activity? Are there other factors you'd like to mention?
4. Can you tell me about your encounters with patients using the CGM?
Probes: How long was the encounter? How did it feel from your perspective? Is there anything you'd like to highlight as working particularly well? Anything you would think about doing differently during these encounters?
5. Were you able to relate the Libre 2 results to things going on in the patients' lives? Were you able to build plans of action with your patients using Libre 2 results?
Probe: How challenging did you find this? What kind of plans did you typically leave with? Did patients need a lot of convincing to take these steps?
6. Do you feel you have the right training or resources to help patients at this stage of their diabetes, to use the CGM and improve their diabetes?
7. Is there anything else you would like to share about help adults with diabetes who are not on insulin use the Libre 2?

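### The isCGM interview guide presumes lifestyle change, the control guide has no matching prompt, and no guide asks about medication change, so the qualitative explanation tilts towards the presumed mechanism (minor, cheap to fix)

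*Combined protocol and SAP*

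**What the plan says.** Section 4 lists, among the secondary objectives, understanding why or how "isCGM with CDE education is effective or ineffective from the perspective of involved participants and their providers". Section 10 says of the interviews: "The starting point will be the participant and provider experience with isCGM or enhanced usual care", with a focus on barriers and enablers.

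Appendix 6 gives three guides.

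- **Group 1 (isCGM participants).** Question 3 asks "What changes did the Libre 2 lead to in terms of what you eat or what you do during the day" and continues "How difficult was it to make those changes". Both of its probes refer back to the same changes. A probe under question 7 raises diet and activity again, this time linked to the educator.
- **Group 2 (enhanced usual care).** Participants are asked about their care before the educator, the educator's impact, the second encounter, glucose testing ("Did you start measuring your blood sugars at any time during the trial"), and their goals. Neither diet nor activity is named.
- **Group 3 (providers).** Question 2 opens "What difference did the Libre 2 make for our trial patients who were not on insulin" and then asks whether the device was useful or not, and why. Diet and activity appear once, in a probe listing patient factors that might determine usefulness.

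Section 17 presumes that any glycemic benefit would come through diet and lifestyle in the isCGM arm, then adds: "An alternative mechanism may be more rapid medication titration based on isCGM data".

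**The concern.** The interviews are the plan's route to an explanation. Section 17 sets out two candidate mechanisms. The guides prompt the presumed one directly, in one arm, in wording that assumes it operated. They do not prompt the other at all.

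A participant who changed nothing has to contradict the question in order to say so. A control participant who changed diet after seeing the educator is not asked. A participant whose medicines were changed after the educator wrote to the usual provider is not asked either. Section 23 says the post-trial work will shed light on what mediates any effect, and that the intervention package will be revised afterwards. An account that reflects the prompts as well as the experience would serve both purposes less well.

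**Working it through.** The plan gives no figure on this point, so the check is a count of questions and a comparison of sections.

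**1. Count of the numbered questions in Appendix 6, with their probes**

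| | Group 1 (isCGM) | Group 2 (control) | Group 3 (providers) | Total |
|---|---|---|---|---|
| Numbered questions | 11 | 6 | 7 | 11 + 6 + 7 = 24 |
| Raise diet or activity | 2 (Q3, Q7 probe) | 0 | 1 (Q3 probe) | 3 |
| Raise *change* in diet or activity | 2 | 0 | 0 | 2 |
| Raise medication change | 0 | 0 | 0 | 0 |

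Provider questions 2 and 7 mention insulin, but only to describe the population as not using it.

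**2. Is the Group 1 wording presumptive?** Compare question 3 with question 4 of the same guide. Question 4 asks whether the Libre 2 changed how the participant thinks or feels, which allows a no. Question 3 asks which changes followed and how hard they were, which does not. Neutral wording was therefore available and was used for feelings but not for behaviour.

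**3. Does the prompt apply to controls?** Section 6 gives both arms two educator encounters with individualized diet and activity advice. Change in diet or activity is thus an expected result of the control condition too. The nearest Group 2 item, a probe under question 1, concerns what the participant was doing before meeting the educator.

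**4. Does the medication omission matter?** Section 6 says that educators in the isCGM arm may send titration recommendations to usual providers at the second encounter. The control description contains no such sentence. As described, medication is a possible source of a difference between arms, and Section 17 recognizes it as one.

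**5. What is covered elsewhere?** Diet (UKDDQ) and physical activity (IPAQ) are measured in both arms at baseline, 6 and 12 weeks, and Section 14 analyses them between arms. Medication names and doses are recorded at baseline (Appendix 5.2) and follow-up (Appendix 5.3), and the follow-up form counts medicines that were new, increased, decreased or stopped. Section 14 states no by-arm summary of these medication data.

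Whether diet and activity changed is therefore covered quantitatively. Medication change is recorded but has no stated analysis. The reasons for any of these changes depend on the interviews.

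**The case against.** The strongest reply is that a semi-structured guide does not limit what is asked, and that these guides contain real openings.

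- Group 1 question 4 is neutral, question 9 asks why or why not, and provider question 2 goes on to invite a negative answer with a probe for it.
- Group 2 question 2 repeats Group 1 question 6 with the same probes, including what was learnt and whether a plan was made. Since the educator advises on diet and activity, lifestyle change could well come up there.
- Provider question 5 asks what plans were made, which could bring out titration.
- Section 17 says the intervention is not intended to give further support for prescribing.

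All of this stands, and it rules out several stronger conclusions that a reader might draw:

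- *That the guides lead to a single answer.* The openings just listed show otherwise.
- *That the thematic analysis is a biased comparison of arms.* Section 14 describes constant comparison as iterative refinement of codes. It plans no contrast of theme frequency by arm.
- *That the loss could not be recovered.* Section 14 provides for periodic review and for further sampling guided by emerging themes, so a medication theme could be pursued in later interviews.
- *That the provider guide fails because it asks only about the sensor.* Section 9 says providers are interviewed for their perspective on the use of isCGM. The mention of enhanced usual care in Section 10 is not enough to require a further provider question.

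What remains is that these openings leave two topics to chance: lifestyle change among controls, and medication change in everyone. Unscripted follow-up also does not neutralize a question that has already assumed its answer.

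**Conclusion.** The concern holds as a minor point. The guides tilt the qualitative explanation towards the lifestyle mechanism: it is prompted in 2 of 11 isCGM questions and 0 of 6 control questions, while the protocol's own alternative is prompted in 0 of 24. These counts measure prompting. They do not measure bias, and the documents give no basis for saying how far the themes would shift. That the themes would shift at all is an inference, resting on the assumption that interviewers largely follow the written questions and probes.

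The effect is confined to one secondary, qualitative objective. The HbA1c analysis, the other quantitative outcomes and the safety comparisons are untouched.

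**What to change.** 1. Keep Group 1 question 3, but word it neutrally, for example: *Did using the Libre 2 change, or not change, your eating or your daily activities? What helped, or got in the way?* It should stay because it is the only direct question on what the sensor changed in behaviour.
2. Add one identical probe to Group 1 question 6 and Group 2 question 2: *Since meeting the educator, has anything changed, or not changed, in what you eat, how active you are, or your diabetes medicines?*
3. Add a medication probe to provider question 5, for example: *Did these plans include, or not include, any change to diabetes medicines?* No new provider question on patients managed without a sensor is needed.
4. Report beside the themes a descriptive by-arm table of glucose-lowering medicines started, increased, decreased or stopped. The counts in Appendix 5.3 cover all medicines, so the glucose-lowering subset should be taken from the names and daily doses in Appendices 5.2 and 5.3.

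If some interviews have already taken place, record which guide version each interviewee received.

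The cost is a revised guide with ethics notification, a few minutes per interview, and one table from data already collected.

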APPENDIX 7: PI-Initiated Study Risk Assessment Worksheet

Appendix C: PI-Initiated Study Risk Assessment Worksheet			

Use this table to assess the risks of the study's procedures, experimental treatments, and population vulnerability to derive an estimate of the overall risk of the study. For each factor please enter the appropriate score and add up. Please note, this assessment will simultaneously undergo a binding independent review through QMCR. Once this form is completed please return it to [name] at QMCR.
			
Study Title: Intermittently Scanned CGM Versus Usual Care With Diabetes Education and Feedback, in Adults with Type 2 Diabetes (iCUDE) PI: [name]		ENTER SCORE	
I. Experimental Treatment			
Low Risk	No experimental treatment in study	1 point	2
Moderate Risk 	Treatment effects documented from studies with similar and/or different populations and/or settings. No serious adverse events expected. Specific plans to monitor AE's detailed in DSMP	2 points	
High Risk	Experimental treatment. (e.g. investigational drug, device, or biologic)	4 points	
II. Procedures, Measurements, and Data Collection Methods			
Low Risk 	Minimally invasive with low degree of emotional and/or physical discomfort. Probability of adverse events is low. Severity (magnitude) of adverse events is low. (Procedure may be rated low risk if probability of AE is moderate to high so long as the severity is low, as in the case of a bruise from phlebotomy) (e.g. procedures that meet IRB criteria for expedited review)	1 point	1
Moderate Risk	Moderate degree of emotional and/or physical discomfort. Probability of adverse events is low. Severity of adverse events is moderate to high. (e.g. PET scan, lumbar puncture, arterial lines)	2 points	
High Risk	Moderate to high degree of emotional and/or physical discomfort. Probability of adverse events is moderate to high. Severity of adverse events is high. (e.g. heart muscle biopsy, insulin infusion)	4 points	
III. Decision-making Capability			
Non-vulnerable 	Adult who 1) demonstrates decision-making capacity and 2) demonstrates no perception of undue influence or coercion to participate.	1 point	1
Vulnerable	Any minor. Adult who 1) demonstrates limitations in decision-making capacity and/or 2) is prone to perception of undue influence or coercion to participate.	2 points	
Review completed by: [name] Signature:			4
Date: Feb 27, 22 TOTAL:			

The Level of Overall Risk of the Study is: Low: 3 or 4 points Moderate: 5 points High: 6 to 10 points
 
Monitoring Requirements:
 
3-5 points: may be monitored by the PI who provides an annual review of data and safety information.
 
6 points: may be monitored by the PI who provides a quarterly review of data and safety information.
 
7-10 points: must have an independent monitor or DSMB, who conducts a regular review of data and safety information.
 
Are there any concerns regarding scientific validity or the probability of obtaining reasonable results?
 
Yes No
			
01OCT2012		Page 1 of 1
